4.5 Stopping Rules

All study agent administration will stop if any of the following events occur during the study:

- Death attributed to study drug;
- Serious systemic anaphylactic tumor injection reaction;

- Serious rare reactions to F-araAMP, such as blindness or coma.

The FDA, Office of Biotechnology Activities/National Institutes of Health (OBA/NIH), IRB and SMC will be notified immediately if one of these AEs occurs and a comprehensive review of the safety data will be conducted prior to resumption of dosing. In addition, findings from the review will be relayed to and discussed between the SMC and Sponsor (GeoVax). Should the SMC and GeoVax agree to stop the study, GeoVax will inform all investigational sites and the appropriate regulatory bodies of the decision to stop the study at all sites.

4.6 Drug Accountability

The investigator will be responsible for dispensing and accounting of Ad/PNP provided by the IND Sponsor. The investigator will also be responsible for documentation of lot numbers, dose and administration of Ad/PNP-F-araAMP given during the study. Under no circumstances will the investigator supply vector to other investigators, allow vector to be used other than directed by this protocol, or destroy or dispose of vector in any other manner without prior authorization from the IND Sponsor.

Any residual vector must be returned to the investigational pharmacy for disposition. The site's Investigational Pharmacy will dispose of all unopened or partially used vials of Ad/PNP at the end of the study. Please see the Pharmacy Manual for full and current details.

4.7 Concomitant Medications

All medications taken at the time of study entry will be recorded. Any changes in concomitant medication, including additions, discontinuations, and dose changes, occurring during study participation will be recorded.

The following concomitant treatments are permitted during the study:

- All supportive measures (including antiemetics, red blood cell transfusions, antibiotics) consistent with optimal patient care will be given throughout the study and should be documented in the case report form (CRF).
- Colony-stimulating factors and erythropoietin may be used during the study if clinically indicated according to the American Society Clinical Oncology guidelines. However,

neither granulocyte colony-stimulating factor (G-CSF) nor granulocyte-macrophage colony-stimulating factor (GM-CSF) will be used prophylactically in this study.

The following concomitant treatments are not permitted during the study:

- Allopurinol
- No systemic anticancer agent other than the study drug
- Palliative radiation therapy (if a subject has need for palliative radiation, they will be removed from the study)
- Subjects that develop symptomatic pleural effusion/pericardial effusion will be taken off study, and treated with standard therapies
- No other investigational therapies or devices will be allowed during study participation.

4.8 Criteria for Removal from Study

Treatment will be stopped and patients will be removed from study due to unacceptable AEs, withdrawal of consent, or non-compliance.

5. INVESTIGATIONAL AGENT/DEVICE/PROCEDURE INFORMATION**5.1 Description of Study Drug**

Study drug for administration to the subjects consists of the vector Ad/PNP for intratumoral administration and F-araAMP for intravenous administration.

F-araAMP (fludarabine phosphate) is licensed as a treatment for hematological malignancies but lacks efficacy to treat solid tumors. In the nonclinical studies, administration of the Ad/PNP vector intratumorally alone had little or minimal activity on tumor size. F-araAMP is being administered as a prodrug where subsequent generation of F-Ade within tumor cells transfected with the vector is expected to have local anti-tumor effect on the solid tumor. Commercial F-araAMP (fludarabine phosphate) available from the site's formulary will be used in this study.

The vector, Ad/PNP, is manufactured by the biologicals manufacturing division of Sigma-Aldrich, SAFC Pharma (Carlsbad, CA).

Ad/PNP will be supplied as a liquid formulation in vials containing 2×10^{11} VP/100 μ l in 20 mM Tris (pH 8.0), 25 mM NaCl, 2.5% Glycerol and should be stored at less than -60° C. Dilutions of the vector in sterile normal saline USP will be made immediately prior to use. Following dilution, the investigational pharmacy will send the vector to the clinic on ice for administration. Vector should be administered as soon as possible after dilution and must be used within 6 hours of thaw. The vector will be administered percutaneously via injection into the tumor mass. A subcutaneous injection of local anesthetic may be used, if desired.

5.2 Availability

Ad/PNP for this project will be furnished by GeoVax, Inc. (Smyrna, GA). Commercially sourced F-araAMP will be used for this study.

5.3 Agent Ordering

Orders for Ad/PNP will be placed with GeoVax by the study team after approval to proceed has been granted by the IRB and Investigational Pharmacy. Ad/PNP will be transported on dry ice by overnight courier to the site's investigational pharmacy.

5.4 Agent Accountability

Each investigator will be responsible for dispensing and accounting of Ad/PNP provided by the IND Sponsor. The investigator will also be responsible for documentation of lot numbers, dose and administration of Ad/PNP-F-araAMP given during the study. Under no circumstances will the investigator supply vector to other investigators, allow vector to be used other than directed by this protocol, or destroy or dispose of vector in any other manner without prior authorization from the IND Sponsor.

Any residual vector must be returned to the investigational pharmacy for disposition. The site's Investigational Pharmacy will dispose of all unopened or partially used vials of Ad/PNP at the end of the study. Please see the Pharmacy Manual for full and current details.

6. DOSE MODIFICATIONS

See Section 4.3 for dose modifications of Ad/PNP and F-araAMP.

7. ADVERSE EVENTS AND REPORTING PROCEDURES

7.1 Adverse Event

An adverse event (AE) is any unfavorable and unintended diagnosis, symptom, sign (including an abnormal laboratory finding), syndrome or disease which either occurs during the study, having been absent at baseline, or, if present at baseline, appears to worsen. For this study, only abnormal laboratory findings with clinical significance as determined by the PI are considered AEs.

A TEAE is defined as an AE with onset occurring at any time point after the first intratumoral administration of Ad/PNP. A TEAE also may be a continuing AE reported prior to the date of the first dose of study drug, which worsens in severity after the first administration of Ad/PNP.

Disease progression is not an AE (non-serious or serious), although signs and symptoms thereof may be reportable as AEs.

7.2 Serious Adverse Event

A SAE (experience) is defined (21CFR312.32) as any adverse experience that suggests a significant hazard, contraindication, side effect, or untoward medical occurrence that:

- Results in death,
- Is life-threatening (Note: the term “life-threatening” refers to an event in which the subject was at risk of death at the time of the event rather than to an event which hypothetically might have caused death if it were more severe.),
- Requires (or prolongs) hospitalization,
- Causes persistent or significant disability/incapacity,
- Results in congenital anomalies or birth defects, or
- Important Medical Event Requiring Medical or Surgical Intervention to Prevent Serious Outcome.

Medical and scientific judgment should be exercised in deciding whether expedited reporting is appropriate in other situations, such as important medical events that may not be immediately life-

threatening or result in death or hospitalization but may jeopardize the subject or may require intervention to prevent one of the other outcomes listed in the above definition. These should be considered serious.

Pregnancy is not considered an AE. However, the medical outcome of an elective or spontaneous abortion, stillbirth or congenital anomaly is considered an SAE and must be reported to the Sponsor within 24 hours of the site becoming aware of the event. The study investigator will make every effort to obtain permission to follow the outcome of the pregnancy and report the condition of the fetus or newborn to the Sponsor.

Any pregnancy which occurs during this clinical trial must be treated as a SAE with regard to the reporting timeline. Any pregnancy must be followed until conclusion of the pregnancy (delivery or termination). Administration of study drug will be discontinued in a subject who becomes pregnant. The subject will be asked to complete safety evaluations through Study Day 56 of the subject's last cycle (no follow-up imaging studies for the purposes of this study will be obtained). If a male subject reports a pregnancy of his spouse or significant other within Day 56 of last study treatment, every effort will be made to obtain data regarding the outcome of this pregnancy.

Pregnancies must be reported using the paper Pregnancy Form. All pregnancies must be followed up until delivery or termination of pregnancy and until final outcome, using the paper Pregnancy Follow-Up Form. Reporting of both the initial pregnancy and the outcome must be done via e-mail to [contact].

7.3 Assessment of Causality

The relatedness of an AE to the study drug is the best estimate of the investigator at the time of the reporting of the causal relationship between the study drug and an AE.

The following study drug relationships will be used for this clinical study:

Unrelated: There is no temporal relationship between the event and the administration of the study drug, and/or the event is clearly due to the subject's medical condition, other therapies, or accident.

Possibly Related: There is some temporal relationship between the event and the administration of the study drug and the event is unlikely to be explained by the participant's medical condition or other therapies.

Probably Related: The temporal relationship between the event and the administration of the study drug is compelling, and the participant's medical condition or other therapies cannot explain the event.

Definitely Related: The temporal relationship between the event and the administration of the study drug is compelling, the participant's medical condition or other therapies cannot explain the event and the event follows a known or suspected response pattern to the medication.

The categories of Definitely, Probably, and Possibly are considered study drug related.

7.4 Severity of the Adverse Event

Adverse events will be graded per National Cancer Institute (NCI) CTCAE v5 (<http://evs.nci.nih.gov/ftp1/CTCAE/about.html>).

- Mild (Grade 1)
- Moderate (Grade 2)
- Severe (Grade 3)
- Life –Threatening (Grade 4)
- Fatal (Grade 5)

7.5 Safety Monitoring and Reporting

7.5.1 Monitoring of Adverse Events

All subjects will be monitored closely for AEs during study participation. Subjects who discontinue prematurely from the study will be encouraged to return for assessment of safety and their physician contacted to obtain follow-up safety information.

The investigator will monitor subjects for the occurrence of AEs throughout their participation in the study and record all observed AEs in the CRF.

Adverse events spontaneously reported by the subject and/or in response to an open question from study personnel or revealed by observation, physical examination, or other diagnostic procedures are to be recorded in the study specific worksheets. Any clinically relevant deterioration in laboratory assessments or other clinical findings, as assessed by the investigator, is considered an adverse event and must be recorded on the appropriate pages of the CRF. Whenever possible, symptoms should be grouped as single syndrome or diagnosis. The investigator should specify the date of onset, maximal intensity, corrective therapy given, outcome, and his/her assessment of causality (i.e., whether the adverse event was related to the study drug) (Section 7.3).

From signing of informed consent through initiation of study treatment, only SAEs considered related to study procedure(s) should be recorded. After initiation of study treatment (Day 1) through Day 56 of the subject's last treatment cycle, all adverse events regardless of seriousness or relationship to study drug should be recorded.

Serious adverse events considered related to prophylactic antibiotic treatment (and not suspected to be related to study treatment) are expected AEs. They should be collected but are not subject to expedited reporting.

Any AE that is not resolved by the end of the study and considered to be potentially related to study drug or was the cause for the subject's withdrawal will be followed as clinically indicated until its resolution, or if non-resolving, until considered stable.

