4.3 Dose Modification

Based on monitoring of efficacy signal from subjects completing treatment, if no anti-tumor activity and no DLTs are observed, GeoVax may increase the dose of vector administered 5-fold from 2×10^{11} VP/dose to 1×10^{12} VP/dose, which was the high dose of vector used in the Phase 1 clinical trial. DLTs will be determined based on the incidence and intensity of AEs and SAEs assessed as being at least possibly related to Ad/PNP-F-araAMP and occurring up to 28 days after initiation of dosing on Cycle 1 Day 0. Formal approval from the Food and Drug Administration (FDA), IRB, and other regulatory offices as needed will be obtained prior to initiating an increase of vector dose. No serious toxicities were detected with this dose of vector (1×10^{12} VP/dose) in the earlier Phase 1 trial.

The total dose of F-araAMP per cycle is lower than that recommended to treat patients with hematological malignancies. Subjects who experience greater than Grade 2 neurotoxicity should be discontinued from treatment and followed for safety. The investigator may decrease the dose of F-araAMP to 15 mg/m^2 or delay administration based on evidence of high grade (CTCAE v5.0 Grade 3 or higher) hematologic or nonhematologic toxicity not recovered to baseline by day 1 of each subsequent cycle, with the exception of isolated lymphopenia, which will not require a dose reduction. Subjects who require further reduction in F-araAMP in the judgment of the investigator, based upon recurrent high grade AEs not resolved by day 1 of the subsequent cycle should be discontinued from treatment and followed for safety. Growth factor support is not to be used prophylactically in this study.

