### 6.6.1 Adverse Events

An adverse event (AE) is any unfavorable and unintended diagnosis, symptom, sign (including an abnormal laboratory finding), syndrome or disease which either occurs during the study, having been absent at baseline, or, if present at baseline, appears to worsen. For this study, only abnormal laboratory findings with clinical significance as determined by the PI are considered AEs. AEs will be recorded from the date of informed consent through the study follow-up period (~ 60 days after last dose of study drug). AEs will be assessed for severity, using the NCI-CTCAE version 5.0, relationship to study treatment, relationship to non-study treatment, and seriousness. Relationship assessments of possibly related or greater are defined to be related. Any missing relationship assessments will be assumed to be related, and any missing severity assessments will be assumed to be Severe/Grade 3. Disease progression is not an AE (non-serious or serious), although signs and symptoms thereof may be reportable as AEs.

A treatment-emergent adverse event (TEAE) is defined as an AE with onset occurring at any time point after the first intratumoral administration of Ad/PNP. A TEAE also may be a continuing AE reported prior to the date of the first dose of study drug, which worsens in severity after the first administration of Ad/PNP.

A serious adverse event (SAE) is defined as any adverse experience that suggests a significant hazard, contraindication, side effect, or untoward medical occurrence that:

- Results in death,

- Is life-threatening (Note: the term “life-threatening” refers to an event in which the participant was at risk of death at the time of the event rather than to an event which hypothetically might have caused death if it were more severe.),
- Requires (or prolongs) hospitalization,
- Causes persistent or significant disability/incapacity,
- Results in congenital anomalies or birth defects, or
- Important Medical Event Requiring Medical or Surgical Intervention to Prevent Serious Outcome.

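### Rises in AE grade are not required to be dated, and the protocol and SAP conflict on when AE recording starts and on pre-dose events that worsen

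*Protocol*

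**What the plan says.** **AE record.** Protocol 7.5.1 lists what is to be specified for each event: "The investigator should specify the date of onset, maximal intensity, corrective therapy given, outcome, and his/her assessment of causality". The list does not include the date of the maximal grade or of any grade change. The same section asks for symptoms to be grouped into one syndrome or diagnosis where possible. It also says: "Any clinically relevant deterioration in laboratory assessments or other clinical findings, as assessed by the investigator, is considered an adverse event".

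**Start of recording.** Protocol 7.5.1 says: "From signing of informed consent through initiation of study treatment, only SAEs considered related to study procedure(s) should be recorded". From Day 1 to Day 56 of the last cycle, "all adverse events regardless of seriousness or relationship to study drug should be recorded". The AE row of the Protocol 9.1 table has no mark at screening. SAP 6.6.1 says instead: "AEs will be recorded from the date of informed consent through the study follow-up period". The SAP's copy of the table (Appendix 2) marks AEs at screening.

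**Treatment emergence.** Protocol 7.1 and SAP 6.6.1 both count as a TEAE a "continuing AE reported prior to the date of the first dose of study drug, which worsens in severity after the first administration". The algorithm in SAP Appendix 1 classes an event with a known start before treatment as not a TEAE, and no branch deals with worsening.

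**DLTs.** Protocol 4.3 says: "DLTs will be determined based on the incidence and intensity of AEs and SAEs". These must be at least possibly related and occur within 28 days of first dosing. The section gives no grade threshold and does not say which date of an event decides. SAP 6.6.1 plans counts and a table of DLTs, and TEAEs by maximum grade. It lists no AE table by cycle.

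**The concern.** The primary objective is the safety of repeat administration, and Protocol 4.4 says that the toxicity of intratumoral F-Ade with repeat injection is unknown. A reader of the final data will want to know whether toxicity became more severe in later cycles. A record with one onset date and one peak grade cannot answer that for an event that starts mild in cycle 1 and turns severe later. The same record leaves DLT assignment open, and Protocol 4.3 makes a possible vector dose increase conditional on there being no DLTs.

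The conflict over the start of recording is a separate defect and does not cause misdating between cycles. It affects events present before the first injection: the worsening clause needs a pre-dose grade, which the protocol does not collect for non-serious events. Such events are plausible. Exclusion 7 bars neuropathy only above Grade 2, and exclusion 6 admits patients who have settled at a new baseline after chemotherapy.

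**Working it through.** **1. The plan's own safety figure.** Protocol 12.1 gives a one-sided 80% upper limit of 0.38094 for 2 events in 10 subjects. The Clopper-Pearson limit is the 0.80 quantile of Beta(x+1, n−x), here Beta(3, 8), which is 0.38094. All 11 rows of the table agree to within 0.00005. The only inputs are n and x, the number of subjects with a treatment-related SAE. No onset date enters, so this criterion does not move.

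**2. Timeline.** Cycles start every 28 ± 3 days, up to five (Protocol 4.2).
- At 28-day spacing, the start of cycle k is 1 + 28(k−1): Days 1, 29, 57, 85 and 113.
- The last infusion is on Day 5 of cycle 5: 113 + 4 = Day 117.
- Day 56 of cycle 5 is 113 + 55 = Day 168.
- With every interval at 25 or at 31 days, the last infusion falls on Day 105 or 129 and the final visit on Day 156 or 180.
- The DLT window covers 28/168 = 17% of observed time, about one cycle of five.

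**3. An event that worsens across cycles (assumed case).** Fatigue starts at Grade 1 on Day 5 and reaches Grade 3 on cycle 3 Day 5, which is 57 + 4 = Day 61. Held as one record, it reads as Grade 3 with onset on Day 5. The severe grade is dated 61 − 5 = 56 days early and appears to lie inside the DLT window. The error would add a DLT, not hide one. With a new record at the grade change, Grade 3 starts on Day 61, in cycle 3 and outside the window.

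**4. Recording before the first injection.**

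| Place | What is recorded |
|---|---|
| Protocol 7.5.1 | procedure-related SAEs only |
| Protocol 9.1, AE row | nothing marked at screening |
| SAP 6.6.1 | AEs from consent |
| SAP Appendix 2, AE row | AEs marked at screening |

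The two text sections conflict on their own, whatever the tables show.

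**5. A pre-dose event that worsens (assumed case: Grade 1 fatigue at screening, Grade 3 in cycle 3).**
- *Recorded as in the SAP, one record per event:* the start is pre-dose, so Appendix 1 returns not a TEAE. The definition in Protocol 7.1 and SAP 6.6.1 returns a TEAE.
- *Recorded as in the protocol:* there is no pre-dose AE record. Medical history (9.3.3) captures current illness but does not ask for a grade. After dosing, the site may enter the worsening with a post-dose start (a TEAE) or with its true original onset (not a TEAE under Appendix 1).
- *A new record at the grade increase:* the Grade 3 record has a post-dose start and is classed as a TEAE.

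**The case against.** The strongest reply is that the protocol can be read as capturing worsening. Section 7.5.1 treats a clinically relevant deterioration as an AE to be recorded, and 9.2.1 says changes are recorded at every visit. The dose-modification text in 4.3 needs toxicity grades at the start of each later cycle. Nothing forbids a new record when the grade rises, and the CRF and the clarification letter on which the SAP rests (SAP section 1) are not available. This stands in part: it shows that grades will be looked at, not that each rise is entered as a dated AE record. The lists for Visits 8 and 9 mention only new and resolved events.

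A reader might infer that DLT timing is wrong. The documents do not support that. Protocol 4.3 gives no grade threshold or onset-date rule, the SAP gives no derivation, and no analysis of DLT timing is planned. Assignment is open to error, but no error is shown. Any dose increase would also need regulatory and IRB approval first.

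A reader might also infer that the timing of all toxicity is lost. It is not. Hematology and chemistry are measured on Days 1 and 14 of each cycle and summarized by time point, so myelosuppression can be dated by visit even though SAP 6.6.2 plans no laboratory grading. Pain, fatigue and neurotoxicity have no such scheduled laboratory series.

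Nor can the problem be sized from the Phase 1 rates of injection site pain (91.7%) and fatigue (66.7%). Follow-up there ran to Day 56, the onsets are not dated to cycle 1, and injection pain may recur as separate events.

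**Conclusion.** The point holds in conditional form for the dating of grades, and without condition for the document conflicts.

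- **Dating.** If the CRF keeps one record per event, the cycle in which non-laboratory toxicity became severe cannot be read from the AE data, and a late severe event could be counted in the DLT window. The share of events that persist and worsen is not given, so the number affected is unknown. In the assumed case the shift is 56 days.
- **Start of recording.** Protocol 7.5.1 and SAP 6.6.1 cannot both be followed. It would be too strong to say that the protocol records nothing before Day 1, because procedure-related SAEs are collected from consent.
- **Treatment emergence.** Appendix 1, applied as written, can drop a worsened pre-dose event that both definitions count as a TEAE.

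No stated figure changes. The treatment-related SAE criterion is unaffected. The changes should be made because the primary objective concerns repeat cycles, and dates of grade change may not be recoverable afterwards.

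**What to change.** 1. **Protocol 7.5.1 and CRF guidance:** require a new AE record with its own start date at each increase in CTCAE grade. Recording the date of maximal grade is a lighter alternative, but it dates only the peak and not the intermediate rises.
2. **SAP 6.6.1:** state that the date on which the qualifying grade began decides whether an event falls in the DLT window. Reconcile Protocol 4.3, which counts from Day 0 of cycle 1, with the schedule, which starts dosing on Day 1.
3. **Start of recording:** reconcile Protocol 7.5.1, the 9.1 table, SAP 6.6.1 and SAP Appendix 2 so that the pre-dose grade is available.
4. **SAP Appendix 1:** add a branch that classes a pre-dose event as treatment-emergent when its grade rises after the first injection.

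The SAP's once-per-participant incidence counts can stay as they are. The cost is a short protocol correction, revised CRF guidance, brief SAP wording, a few more AE lines per subject and some added recording at screening. No treatment rule changes.
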